7.3 Study population

7.3.1 Eligibility criteria

Participants fulfilling all of the following **inclusion** criteria are eligible for the study:

Study 1:

- Pregnant women (≥ 18 years of age) with gestational age ≤ 20 weeks
- Written Informed Consent as documented by signature

Study 2:

- Children 6-35 months of age at recruitment
- Written Informed Consent as documented by signature

The presence of any one of the following **exclusion** criteria will lead to exclusion of the participant

Study 1:

- Family does not intend to stay within the study area for at least the following 30 months
- Known history of allergy towards peanut or milk products
- Visible severe disease

Study 2:

- Family does not intend to stay within the study area for at least the following 24 months

- Visible severe disease

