Study 2 Luhya (version 2)	42
14.2 Questionnaires/assessment forms	43
Enrolment form study 1	43
Round 1 form study 1 (version 2)	43
Round 2 form study 1 (version 2)	43
Round 3 form study 1 (version 2)	43
Round 4 form study 1 (version 2)	43
Round 5 form study 1 (version 2)	43
Monthly adherence and morbidity questionnaires study 1	43
Referral form study 1	43
Enrolment form study 2	43
Round 1 form study 2	43
Round 2 form study 2	43
Round 3 form study 2	43
Quarterly adherence and morbidity monitoring questionnaire study 2	43
Referral form study 2	43
Adverse event reporting form study 1 & 2	43
Serious adverse event reporting form study 1 & 2	43
14.3 Curriculum vitae of investigators and certificates	43
14.4 IRB approval letter from PI's country	43
14.5 Signed government approval letter	43
14.6 Pharmacy and Poisons Board retention certificate & Import Permit for LNS	43

ABSTRACT

Background: In Kenya, 26% of children under-five years of age are malnourished, and 26% of pre-school children, 26% of women of reproductive age and 42% of pregnant women are anaemic, respectively. Agriculture is the main source of income and food for the majority of rural families in Sub-Saharan Africa including Kenya. Agricultural programmes have led to increased yield and household income but had limited success in improving nutritional status.

Objectives: To assess the impact on growth and micronutrient status of an integrated programme by introducing nutrition-specific (e.g. micronutrient supplements) and nutrition-sensitive (improved water, sanitation and hygiene, e.g. chlorine, soap) components to an existing agricultural programme.

Methods: The impact of the integrated programme will be assessed in two cluster-randomized intervention studies comparing one group receiving the integrated intervention to another group receiving the agricultural intervention alone (control arm):

Study 1: cluster-randomized, parallel-group, prospective, follow-up effectiveness study in pregnant women and their offspring

Study 2: cluster-randomized, parallel-group, prospective, follow-up effectiveness study in children 6-59 months old

Study duration: The fieldwork of study 1 will take place over approximately 2.5 years (April 2018-December 2020), while the duration for study 2 will be approximately 2 years (February to 2018-March 2020).

Budget: The budget for conducting the two studies is \$ 2,055,458.

ABBREVIATIONS

1AF	One Acre Fund
AE	Adverse Event
AGP	Alpha 1- acid glycoprotein

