7. STUDY DESIGN AND SAMPLING STRATEGY

7.1 Study design and sampling procedures

Study 1:

General study design: Study 1 is a cluster-randomized, parallel-group, prospective, follow-up effectiveness study over a period of 1000 days comparing 2 groups:

- a) Intervention group: **Pregnant women** will be given LNS (1 sachet/day), raw eggs (2/day), and an anthelmintic drug (albendazole) in the second trimester of pregnancy, as well as soap and chlorine solution for the woman and the household. After delivery these products will be continued until the child reaches 6 months of age. Thereafter, LNS and eggs for mothers and anthelmintic drugs will be discontinued and instead, the **child** will receive LNS (1 sachet/day), one egg/day and Oral Rehydration Salts (ORS) along with zinc tablets (20 mg/day) for treatment in case of acute diarrhoea. These products will be given until the child reaches 2 years of age. The products will be accompanied by life stage-appropriate nutrition and WASH trainings (pregnancy, lactation, infant and young child feeding), as well as SMS reminders to highlight certain messages on antenatal care and nutrition. All products and trainings will be

provided free of charge. The households in the intervention group will also have the same agricultural intervention as the control group.

- b) Control group: All households will be provided with agricultural training (every 2 weeks on average) for free. In addition, households can also enrol for the following products on credit: compost booster, cook stoves, seeds (onions, maize, indigenous greens, beans), maize storage bags, drying tarps, trees, solar lights, fertilizer, actellic dust (insecticide), re-usable sanitary pads.

We anticipate recruiting 1200 (600 in each group) pregnant women into the study (see section 7.2 for sample size calculation); this is expected to yield a sufficiently large sample of children later in the study. Women will be recruited from 120 clusters (randomly assigned to intervention or control) that will be drawn from from Kimilili and Webuye districts in Bungoma County in Western Province of Kenya.

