We anticipate recruiting 1,200 (600 in each group) pregnant women into the study (see section 11.2 for sample size calculation); this is expected to yield a sufficiently large sample of children later in the study. Women will be recruited from 120 clusters (randomly assigned to intervention or control) that will be drawn from from Kimilili and Webuye districts in Bungoma County in Western Province of Kenya.

The communities will be informed about the study in village meetings by CHVs and by conducting outreach within their catchment area to identify pregnant women. Pregnant women will then be screened by 1AF enumerators. During **screening**, a few questions on health status and pregnancy will be asked. If the woman is prior or equal to 20 weeks of gestation (according to last menstrual period), has no visible severe disease and no allergy to peanuts or milk products, and confirms anticipated residence in the area for the coming 30 months, written informed consent for her and her offspring will be sought from her. She will then be asked to provide a urine sample to confirm pregnancy and she will be enrolled if pregnancy is confirmed. Following the screening, 5 assessment rounds (baseline and 4 follow-up assessments during the intervention) will be conducted at the participant's homes (rounds 1-3) or at a central place (rounds 4 and 5) within walking distance from their homes (Figure 2). Assessment round 3 (immediately) after delivery will be conducted as home visits or clinic visits in case of delivery at a clinic. Details of assessment procedures for each round are illustrated in (Figure 3).

Round 1 (Enrolment, ≤ 20 wk of gestation):

On the day of enrolment the round 1 assessment will be done. As part of this, the following information will be collected: household demographics and characteristics, maternal education; knowledge, attitude and practices (KAP) of specific dietary and nutrition practices during pregnancy; individual dietary diversity; antenatal care; WASH practices; height, weight and mid-upper arm circumference; maternal haemoglobin concentration and malaria parasitaemia from a capillary blood sample. After round 1, participants randomly allocated to the intervention group will start receiving the intervention package.

Round 2 (Gestational age of 34 ± 1 wk):

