In round 2, interview questions related to diet and nutrition KAP during pregnancy, dietary diversity, antenatal care, and WASH will be asked. Additionally, MUAC (mid-upper arm circumference) will be measured and a capillary blood sample for measurement of haemoglobin concentration, malaria parasitaemia and micronutrient status will be provided.

Round 3 (Within 24-48 hours after delivery):

The mother-child pair will be visited within 24-48 hours after delivery. The following information will be recorded: delivery date and time, delivery method, recent antenatal care, and early initiation of breastfeeding. The mother will be assessed for MUAC but no blood sampling will be conducted. For the newborn, head circumference, birth weight and birth length, and haemoglobin concentration (from a heelprick) will be measured.

Round 4 (At 6.5 mo ± 1 mo of age of offspring):

This assessment will be conducted when the child turns 6.5 months old. Breastfeeding and other infant and young child feeding indicators, child morbidity, maternal dietary diversity, postnatal care, and WASH information will be gathered. In mothers, MUAC and weight will be measured and haemoglobin concentration and malaria parasitaemia from a capillary sample will be assessed. In

children, length, weight and head circumference will be measured and a capillary blood sample for haemoglobin concentration, malaria parasitaemia and micronutrient status will be provided.

Round 5 (At 24 ± 1mo of age of offspring):

This assessment will be conducted when the child turns 24 months old. Questionnaire-based information on child feeding, child dietary diversity, child morbidity and WASH will be collected. As in round 4, child length, weight and head circumference will be measured and a fingerprick blood sample will be provided for the measurement of haemoglobin concentration, malaria parasitaemia, and micronutrient status. No maternal biomarkers will be collected at this point.

As part of the monthly visits to the participants' households, the CHV will also collect data on intervention adherence and recent morbidity.

[figure not shown]

Figure 2: Timing of assessment rounds for study 1.

[figure not shown]

Figure 3: Detailed procedures for each assessment round in study 1

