To ensure a high quality of data collection, SOPs will be developed for the different persons involved in the study (SOPs for interviewers, phlebotomists, anthropometrists, team leaders and supervisors). Questionnaire-based data as well as anthropometric and blood-based data will be collected electronically in the field. That way real-time data monitoring will be conducted on an on-going basis in order to provide immediate feedback to the data collectors in case of sub-optimal data quality. In detail, all questionnaire-based data will be collected electronically using tablets and multiple forms for each study visit. They will be directly captured in a tablet. A paper form will be used for the collection of anthropometric and blood sampling results data as this will partly take place at a central place and will be recorded by other people than the questionnaire-based information. This also ensures source data to be available for the primary and main secondary indicators. Anthropometric and blood sampling data and results will be data entered into the tablet in the evening by the interviewer. All electronically captured data will be transferred to the appropriate password secured CommCare platform and will be available for data monitoring, cleaning and analysis for specific investigators.

The CommCare interface enables to enter validation conditions for each question/parameter, which will be set in order to minimise the entry of wrong data (e.g. limiting the entry for gestational age to 2-45). The data will also be checked in the CommCare database. Additionally, regular back-checks will be conducted. For these, 10-15% of participants will be randomly re-surveyed on a selected subset of

questions to assess errors. Any enumerator with high error rates will be held back for retraining. Enumerators found falsifying data through the back-check process will be fired.

Currently, a pilot study mimicking study 1 recruitment and distribution of interventions is being conducted and results will be taken into account in the final planning and training of field staff of study 1.

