12.3 Timelines

The detailed schedule of the two studies is outlined below (Table 12). The training of study 2 staff is planned to start in late January while the training for study 1 is planned for April.

Table 12: Gant chart

Phase	Activities	2017					2018					2019					2020					2021													
		J	F	M	A	M	J	J	A	S	O	N	D	J	F	M	A	M	J	J	A	S	O	N	D	J	F	M	A	M	J	J	A	S	O
Preparatory phase	Elaboration of study instruments																																		
	Submission to ethical committees																																		
	Anticipated clearance from ethics																																		
	Supply procurement																																		
	Recruitment and training of field teams																																		
	Questionnaires pre-testing and translation																																		
Study 1 (1000d)	Enrollment and Baseline (R1)																																		
	Midpoint assessments (R2, R3, R4)																																		
	Endpoint assessment (R5)																																		
	Monthly adherence and morbidity monitoring																																		
	Laboratory analysis																																		
	Data analysis																																		
Study 2 (US)	Baseline assessment (R1)																																		
	Midpoint assessment (R2)																																		
	Endpoint assessment (R3)																																		
	Quarterly adherence and morbidity monitoring																																		
	Data analysis																																		
Qualitative assessment	Data quality monitoring																																		
	Data analysis																																		
Program assessment	Review of management and costing systems																																		
	Routine data collection by implementers																																		
	Data analysis																																		
Reporting	Baseline reports																																		
	Intermediary report																																		
	Final report of operations																																		
	Preparation of final report and journal article/s for publication																																		

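### Study 1's 30-month residence criterion and stated fieldwork period do not cover the 24 ± 1 month primary assessment for every eligible woman

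*Protocol*

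**What the plan says.** Protocol 7.3.1 admits "Pregnant women (≥ 18 years of age) with gestational age ≤ 20 weeks" and sets no lower gestational limit; pregnancy is confirmed by a urine test. The data-entry check given as an example in 8.1, "limiting the entry for gestational age to 2-45", would not block very early gestations either.

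The residence rule appears twice. In 7.3.1 a woman is excluded if "Family does not intend to stay within the study area for at least the following 30 months". In 7.1 she is eligible at screening if she "confirms anticipated residence in the area for the coming 30 months".

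The final assessment is tied to the child's age: "Round 5 (At 24 ± 1mo of age of offspring". The primary outcome in 7.2 is change in LAZ from birth to 24 months. Section 7.1 calls the design a "follow-up effectiveness study over a period of 1000 days comparing 2 groups".

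On the calendar, the abstract states: "The fieldwork of study 1 will take place over approximately 2.5 years (April 2018-December 2020". Section 7.2 bases the sample size on what can be recruited in three months. Section 12.3 dates staff training: "while the training for study 1 is planned for April".

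Section 9.2.4 leaves children without both paired measurements out of the change analysis and assumes that drop-outs resemble completers. Section 7.3.3 states that participants are not replaced.

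**The concern.** The time from enrolment to the primary measurement depends on gestation at enrolment: the earlier a woman enters, the longer her family must stay. A single figure of 30 months suits the late end of the eligible range and not the early end. A family that already plans to leave at month 30 passes screening, although its child's 24-month measurement may fall later.

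The calendar can act in the same direction. Women enrolled early in gestation near the end of recruitment have the latest round 5 dates.

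Any such loss would not be random. Section 5 lists gestational age at enrolment among the variables expected to influence outcome. Table 2 expects earlier enrolment to favour growth because the intervention lasts longer. With an analysis restricted to complete pairs, loss related to that variable strains the assumption in 9.2.4.

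**Working it through.** **Inputs.** From the protocol: gestational age (GA) at enrolment up to 20 weeks, residence 30 months, round 5 at 23 to 25 months, recruitment three months, fieldwork April 2018 to December 2020. Assumed: birth at 40 weeks (37 and 42 also shown). One month = 365.25/12 = 30.44 days.

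**Residence.** Months needed = (40 − GA) × 7/30.44 + child's age at the visit.

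| GA at enrolment (weeks) | to 23 months | to 24 months | to 25 months |
|---|---|---|---|
| 20 | 27.6 | 28.6 | 29.6 |
| 14 | 29.0 | 30.0 | 31.0 |
| 12 | 29.4 | 30.4 | 31.4 |
| 8 | 30.4 | 31.4 | 32.4 |
| 5 | 31.0 | 32.0 | 33.0 |
| 4 | 31.3 | 32.3 | 33.3 |

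The protocol does not derive its 30 months. The figure is consistent with the latest permitted enrolment (20 weeks to the end of the window, 29.6 months).

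The GA below which 30 months is too short is 40 − (30 − age) × 30.44/7:
- to 24 months: 40 − 6 × 30.44/7 = 13.9 weeks (10.9 for birth at 37 weeks, 15.9 at 42);
- to 23 months: 40 − 7 × 30.44/7 = 9.6 weeks (6.6 to 11.6).

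The largest shortfall to 24 months, at GA 4 to 5 weeks, is 2.0 to 2.3 months, or 2.5 for GA 5 weeks with birth at 42. To 23 months it is 1.0 to 1.3 months.

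The design period is 1000/30.44 = 32.9 months, which also exceeds 30.

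**Fieldwork.** From 1 April 2018 to 31 December 2020 is 33.0 months (2.75 years), not 2.5 years. Even if every woman enrolled at 20 weeks, three months of recruitment plus follow-up to 24 months takes 3 + 28.6 = 31.6 months, and to 23 months 30.6. Both exceed 30 months.

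Against 31 December 2020, with birth at 40 weeks:

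| Enrolled | months available | 24-month date missed if GA below | whole window missed if GA below |
|---|---|---|---|
| 1 April 2018 | 33.0 | 0.8 weeks | none |
| 31 May 2018 | 31.0 | 9.4 weeks | 5.0 weeks |
| 30 June 2018 | 30.1 | 13.6 weeks | 9.3 weeks |
| 31 July 2018 | 29.0 | 18.1 weeks | 13.7 weeks |

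The last row applies if recruitment starts at the end of April. That is plausible, since 8.1 places training and a pilot before fieldwork.

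**Illustration only.** GA is assumed uniform from 5, 8 or 12 weeks to 20, and enrolment uniform over three months.

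| Lowest GA (weeks) | start 1 April: 24-month date / whole window after December 2020 | start 30 April: same |
|---|---|---|
| 5 | 20% / 5% | 43% / 19% |
| 8 | 11% / 1% | 32% / 10% |
| 12 | 2% / 0% | 17% / 1% |

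**Power.** The plan's retention is 0.95 × 0.80 × 0.95 × 0.75 = 0.5415, which reproduces its 46% loss. That leaves 600 × 0.5415 = 324.9 per arm, or 249.9 after dividing by the design effect of 1.3. The detectable effect is (1.960 + 0.842) × √(2/249.9) = 0.251 (stated 0.26), and power at 0.26 is 0.83. A further loss of 5%, 10% or 20% would give 0.81, 0.79 or 0.74.

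**The case against.** The strongest reply is that the residence rule is a minimum intention asked at screening, not a cap on follow-up. No section stops visits at month 30, and round 5 follows the child's age. A reader might infer that children of women enrolled early will be lost; the documents do not support that. On the uniform assumptions, 24 to 60% of women need more than 30 months to reach the second birthday, and 0 to 30% to reach 23 months. Those are women for whom the rule is too short, not children lost. The exposed group is families already planning to leave within the gap, and the protocol gives no data on them.

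A reader might also infer that December 2020 is too early for early-pregnancy enrolment as such. It is not: a woman enrolled on 1 April 2018 at 5 weeks has a child turning 24 months about 1 December 2020. The calendar fails only when early gestation meets late enrolment or a delayed start. The dates are called approximate. The Gantt chart has columns in 2021, but its bars are not readable in the text available, so nothing shows that visits cease on 31 December 2020.

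Two further inferences are unsupported. Section 7.2 does not break its 25% child loss down by cause, so it cannot be said to leave this cause out. The rule is the same in both arms, so no bias between arms is shown.

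These replies limit the certainty and size of any loss. They leave standing the mismatch between the enrolment range, the visit window, the residence rule and the calendar.

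**Conclusion.** The point holds as an inconsistency that should be corrected, not as a demonstrated loss. With birth at 40 weeks, 30 months does not reach the second birthday for enrolment before about 14 weeks, or the start of the visit window before about 9.6 weeks. It also disagrees with the 1000-day design. The abstract's duration and dates contradict each other, and the dates may not reach round 5 for women enrolled both early in gestation and late in recruitment.

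Some primary outcomes may therefore be lost in relation to gestational age at enrolment. How many cannot be derived, because the protocol gives no distribution of gestation at enrolment. The 0 to 19% with their whole window after December 2020 rests on assumed uniform distributions, assumed start dates and a literal end on 31 December 2020. The effect on power would be slight at the low end of that range. Near the high end, power would fall to about 0.74, if the loss came on top of the planned attrition.

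**What to change.** In 7.1 and 7.3.1, word the Study 1 criterion as intending to stay until the child is 25 months old, which is up to about 33 months from enrolment. Restate Study 1 fieldwork as ending when the last enrolled child completes the round 5 window, and bring the abstract's duration and dates and the Gantt chart in 12.3 into line with that. As a guide, for a woman enrolled on 30 June 2018 at 5 weeks the child turns 24 months about 1 March 2021, and the window closes about a month later.

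The cost is small: a few more families may be excluded at screening, and there would be a short tail of round 5 visits.
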